## 1.0 INTRODUCTION

Patients with Myelodysplastic Syndromes (MDS) who are red blood cell (RBC) transfusion dependent are known to have a shorter survival in comparison to other MDS patients who do not require RBC transfusions.(1) In addition, there are substantial economic burdens to continued RBC transfusion support(2). While erythroid stimulating agents (ESA, eg, exogenous erythropoietin) are effective in some patients with MDS, many patients do not respond and among responders the duration of response on average is one year (3;4). Lenalidomide is effective in reducing RBC transfusion requirements with a 67% transfusion independence rate in patients with deletion of the long arm of chromosome 5 [del(5q)] MDS(5); however in non-del 5q MDS the response rate is only 27%(6). It is clear that new therapies are needed in this population. Iron chelation therapy (ICT) has been shown to improve hematologic parameters in patients with MDS and in some series there is a demonstrated survival benefit to ICT. Therefore, we propose a phase II prospective trial using ICT with oral deferasirox in patients with MDS with anemia.

## 2.0 BACKGROUND

[figure not shown]
### 2.1 Study Disease

MDS represents a group of clonal myeloid stem cell disorders with a heterogeneous spectrum of presentation, ranging from an indolent course over several years to rapid progression to acute myeloid leukemia (AML). MDS typically occurs without a known preceding insult (*de novo* MDS)(7), but can also occur after chemotherapy or radiotherapy resulting in secondary MDS. The natural history of patients with MDS is varied with a median survival ranging from 8.8 years for patients with very low-risk IPSS-R (Revised International Prognostic Scoring System) scores, to 0.8 years for those with very high-risk scores(8).

The cornerstone of therapy, particularly for lower-risk disease, is centered on improving hematologic parameters thereby reducing the morbidity and mortality associated with low blood counts. At the time of diagnosis over 80% of patients with MDS are anemic, and 50% have a hemoglobin level < 10 g/dL(9). RBC transfusion support is currently the primary management option for MDS-related anemia(2). Transfusions are almost universally effective, ameliorate the patient's symptoms rapidly, and improve health-related quality of life. However, long-term RBC transfusion support can lead to iron overload, which has been associated with an inferior outcome in patients with MDS(1). Strategies to reduce transfusion requirements and subsequent iron overload are imperative to reduce potential harm and to reduce economic and societal costs associated with increased RBC transfusion burdens in MDS patients(2).

[figure not shown]
### 2.2 Clinical Data to Date

Other strategies are used to treat MDS-related anemia. Erythropoiesis stimulating agents (ESA; such as erythropoietin or darbepoetin) are the most commonly used agents to treat MDS(10). However, the benefit of ESA are largely restricted to patients with lower erythropoietin levels and minimal RBC transfusion requirements in the presence of low or intermediate risk disease(11). In approximately 5% of patients, del(5q) is the sole cytogenetic abnormality(12). Lenalidomide has been proven to be an effective agent in this population with 67% of the patients achieving transfusion independence in a phase III trial(5). In the absence of the del(5q) abnormality, the rate of transfusion independence is approximately 27% (6). There is data to indicate that combined therapy with lenalidomide and ESA result in improved erythroid responses(13). Combination therapy with lenalidomide and ESA are under current investigation in a multi-center trial phase III randomized trial. Hypomethylating agents (HMA: azacitidine and decitabine) target the aberrant DNA methylation seen in MDS and result in a response in approximately 50% of patients with low-risk MDS (14;15). Azacitidine is FDA-approved for all stages of MDS. Decitabine is not FDA-approved for patients with low risk disease by the original International Prognostic Scoring System (IPSS)(16). While these agents have been shown to alter the natural history of advanced MDS; there is less data to support their routine use in lower risk MDS patients (17;18). Since the route of administration is either IV or SQ and there is significant toxicity, the HMA are generally not the preferred therapeutic choice for patients with early stage MDS.

**Figure 1:** Survival among 426 patients with low risk MDS according to transfusion dependency.

patients treated conventionally or after stem cell transplantation (1;20-25). In a retrospective analysis from 426 patients with low risk MDS the burden of RBC transfusions was significantly associated with overall survival (**Figure 1**). All patients were diagnosed with MDS based upon the WHO criteria between 1992 and 2004. This data set included patients with a diagnosis of RA, RCMD, RARS, or Del 5q (all with less than 5% blasts). Thus, indicating that even among patients who are traditionally thought to have low risk MDS, RBC transfusion dependence was strongly predictive of survival. This finding led to the development of a dynamic prognostic system known as the WHO-based prognostic scoring system (WPSS) which incorporated RBC transfusion dependence(26). Separately, several investigators found that ferritin serum levels were associated with overall survival in low risk MDS(21). In a retrospective analysis, ferritin levels were available in 95 patients with low risk MDS. When stratified by > or  $\leq$  serum ferritin level of 1,000 ng/mL, MDS patients with higher ferritin levels were found to have an inferior survival (**Figure 2**).

**Figure 2:** Impact of ferritin levels on survival in low risk MDS patients.

analysis(29). In addition, several trials have confirmed the ability of deferasirox to reduce iron content as measured by serum ferritin and in some patients to improve hematologic parameters (32-36). However, all of these studies are non-randomized and most are retrospective. Currently, there is a prospective randomized controlled trial evaluating the use of iron chelation therapy in red cell transfusion dependent MDS patients (TELESTO). In the absence of randomized prospective studies controversy still surrounds the implementation of ICT for patients with MDS.

In the absence of widely effective interventions, MDS-related anemia is often mitigated with RBC transfusions. Although it can relieve symptoms, overtime alloantibodies and iron overload can result as a consequence of multiple transfusions(2). Some patients with MDS, in particular RARS, develop iron overload in the absence of multiple transfusion. This may occur through several mechanisms including ineffective erythropoiesis resulting in increased gastrointestinal absorption(19). Concomitant hemochromatosis gene mutations (HFE) and polymorphisms in other regulators of iron metabolism may also influence the predisposition for iron overload in patients with MDS. Consequently, in certain patients with MDS (RARS), iron overload may not correlate well with the number of RBC transfusions and may occur early in the course of disease.

Several reports have noted a higher mortality rate in multiply RBC transfused, iron-overloaded MDS patients (1;20-25). In a retrospective analysis from 426 patients with low risk MDS the burden of RBC transfusions was significantly associated with overall survival (**Figure 1**). All patients were diagnosed with MDS based upon the WHO criteria between 1992 and 2004. This data set included patients with a diagnosis of RA, RCMD, RARS, or Del 5q (all with less than 5% blasts). Thus, indicating that even among patients who are traditionally thought to have low risk MDS, RBC transfusion dependence was strongly predictive of survival. This finding led to the development of a dynamic prognostic system known as the WHO-based prognostic scoring system (WPSS) which incorporated RBC transfusion dependence(26). Separately, several investigators found that ferritin serum levels were associated with overall survival in low risk MDS(21). In a retrospective analysis, ferritin levels were available in 95 patients with low risk MDS. When stratified by > or  $\leq$  serum ferritin level of 1,000 ng/mL, MDS patients with higher ferritin levels were found to have an inferior survival (**Figure 2**).

Based on preclinical and clinical data, mechanisms underlying the inferior survival in this population point to excess in labile plasma iron (LPI) as the putative mediator(19). This has prompted the use of ICT to modify the negative effect of iron overload in patients with MDS. Although several reports suggest a survival benefit with ICT (27-31), all of them were non-randomized comparisons and were susceptible to a significant selection bias. We know that patients are selected to receive ICT on the basis of an expected survival; otherwise, they would not live long enough to benefit. Therefore, the improved survival in patients treated with ICT could be completely due to a selection bias that is not necessarily overcome by a matched pair

In a multicenter, open-label, single-arm, 3-year phase II trial (US03), the safety and tolerability of deferasirox was evaluated in lower-risk MDS who had received at least 20 units of RBC and had a serum ferritin  $\geq 1,000 \mu\text{g/L}$ (34). Of the 173 patients that underwent ICT with deferasirox, 51 (28%) experienced hematologic improvement, only seven of which received other MDS related therapy. Therefore, ICT appears to improve hematologic parameters in some MDS patients with iron overload. Mean labile plasma iron (LPI) was measured at baseline in 163 patients, among these patients 68 had elevated levels ( $>0.5 \text{ LPI units}$ ). Concentrations of LPI fell within normal limits in all 47 patients who were assessed at week 13 and remained in the normal range through the duration of the trial (Figure 3). Additionally, there was a decline in the median serum ferritin by 23.2% at one year in the patients who completed at least one year of ICT. Therefore, deferasirox was able to reduce the iron burden in iron-overloaded MDS patients.

[figure not shown]

Figure 3: Mean LPI over 12 months in MDS patients with abnormal LPI at baseline.

The annual discontinuation rates of deferasirox were 45%, 43%, and 35% during years 1, 2, and 3 respectively. The safety profile of deferasirox in this setting was reasonable with discontinuation in 43 patients (24.8%) because of adverse events (such as gastrointestinal disturbances) or disease progression and 23 patients (13.2%) because of abnormal laboratory values (such as increased serum creatinine). All 28 deaths that occurred during the study were considered unrelated to deferasirox.

[figure not shown]

Figure 4: Mean change in serum ferritin and mean deferasirox dose among MDS patients in the EPIC Trial

adverse events were gastrointestinal including diarrhea, nausea, vomiting, etc. There were 26 deaths in the study with most common cause being infection. None of the deaths were felt to be drug related. Serum ferritin levels significantly decreased from baseline after 1 year of deferasirox with a median reduction of 606 ng/mL (Figure 4). A post-hoc analysis demonstrated that erythroid, platelet and neutrophil responses were observed in 21.5%, 13%, and 22% of the patients after a median of 109, 169 and 226 days, respectively (Figure 5)(33).

The improvement seen in hematologic parameters after the initiation of ICT may be a result of improved function of the renal oxygen sensing system for erythropoietin production, reducing the inhibitory effect of oxidative stress on hematopoiesis, or

[figure not shown]

Figure 5: Percentage of MDS patients with hematologic improvement enrolled into the EPIC trial

altering intracellular levels of the nuclear transcription factor NF- $\kappa$ B(19).

There is little clinical data regarding ICT in patients who have received minimal RBC transfusions or in patients with a serum ferritin < 1000 ng/mL. However, these patients may still derive benefit from ICT. As discussed earlier, patients with MDS may be more susceptible to iron overload or have iron overload in the absence of multiple RBC transfusions. Furthermore, ICT may modify disease risk beyond RBC transfusion-related events. ICT in the setting of multiple RBC transfusions for other hematologic conditions such as beta-thalassemia major exerts a survival effect largely through reduction in iron-related end organ damage. However, the expected survival in MDS at baseline, even in the setting of lower-risk disease, is on the order of a few years. Given this short timeframe in contrast to the time required to develop RBC transfusion-related end organ damage, the poorer outcome associated with iron overload in MDS may not be entirely accounted for by this mechanism. Iron overload in patients with MDS has been linked according to several studies to increased infection risk and accelerated transformation to AML in addition to end organ damage (28;37;38). By reducing LPI, ICT may decrease the rates of infection and leukemic transformation, and may result in selective toxicity towards MDS hematopoietic progenitors relative to normal progenitors(19). There is also the possibility that mild iron deficiency may mitigate the ineffective erythropoiesis of MDS since emerging data suggest that ineffective erythropoiesis is due, at least in part, to an excess of heme relative to globin as red cells mature and heme toxicities. Reducing iron and thus heme in maturing red cells might correct this imbalance. With a manageable side effect profile along with its disease-modifying potential it is reasonable to explore the efficacy of aggressive ICT with deferasirox in lower risk MDS patients who do not necessarily have excessive iron burden according to ferritin levels.

### **2.3 Study Agent**

Patients will receive oral deferasirox which has been approved by the FDA for the treatment of chronic iron overload due to blood transfusions in patients 2 years of age or older. Deferasirox will be administered to achieve a ferritin < 100 ng/mL and, since it is approved for chelation and used regularly for this purpose as a standard of care, the dosing and schedule will be at the discretion of the treating clinician based on overall iron loading (ferritin), renal function, hepatic function, blood counts, and clinical condition / performance status. Contraindications include the following: Serum creatinine greater than two-times the upper limit of normal (ULN) or glomerular filtration rate (GFR) of less than 40 mL/min, poor performance status, high risk MDS, advanced malignancies, platelet count of less than 50,000, pregnancy, and/or known hypersensitivity to deferasirox.

### **2.4 Risks/Benefits**

The most frequently occurring adverse reactions are diarrhea, vomiting, nausea, abdominal pain, skin rashes and increases in serum creatinine. Among patients with MDS, the major observed toxicity was an increase in serum creatinine (37%). The most frequent adverse reactions that led to drug discontinuation were increase in serum creatinine, diarrhea, nausea, rash and vomiting. Death was reported in the first year in 8% of the patients. Auditory and ocular disturbances occurred in <1% of participants. Deferasirox is considered pregnancy Category C by the FDA as animal studies have demonstrated potential embryonal fetal toxicities with decreased offspring viability with renal anomalies. The potential benefits of deferasirox are reduction in total body iron with improvement in organ function (liver and heart). Additional benefits include the potential to improve hematopoiesis and bone marrow function in general.

## **3.0 STUDY OBJECTIVES**

### **3.1 Primary Objectives**

The primary objective is to assess the activity of ICT with deferasirox in patients with anemia due to MDS.

### **3.2 Secondary Objectives**

Secondary objectives include a reduction in RBC transfusion requirements, hematologic improvement, change in serum ferritin levels from baseline to the end of the study as measured on a monthly basis and safety and tolerability of deferasirox.

### **3.3 Exploratory Objectives**

Samples will be taken to study erythropoiesis and the impact of iron overload on erythropoiesis on patient samples including blood and marrow.

## 4.0 STUDY DESIGN

### 4.1 Description of Study

This study is a single-center open-label prospective phase II trial evaluating deferasirox in patients with very low, low or intermediate risk MDS by the IPSS-R criteria(8).

### 4.2 Endpoints

#### 4.2.1 Primary Endpoint

The primary endpoint is the proportion of patients that achieve erythroid hematologic improvement as defined by the modified IWG response criteria at 6 months(39).

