#### 2. Treatment phase (up to 52 weeks: Day 1 to Week 26)

Patients will receive deferasirox at a starting dose at the discretion of the treating clinician based on baseline serum ferritin levels, renal function, hepatic function, blood counts, and clinical condition / performance status. The target ferritin level is < 100 ng/mL. The primary endpoint of hematologic improvement in the erythroid lineage will be assessed at 6 months. Nonresponders will be offered the option of alternative treatments including clinical trials if available. The maximum duration of therapy on this protocol is one year.

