#### 7.4 Duration of Follow-Up

Patients will remain treated on study for a maximum of one year. The primary endpoint of hematologic improvement in the erythroid lineage based upon the modified IWG criteria (**Appendix G**) will be assessed at 6 months. At the end of 6 months patients who do not respond will be offered the option of alternative treatments including enrollment into clinical trials if possible. The goal is for patients to complete at least 6 months of therapy; however, patients may be removed/withdrawn from the study prior to 6 months as detailed in Section 7.7. Patients will be followed for 30 days following last dose of study related therapy. At the end of one year patients may continue to receive deferasirox but not as part of this trial and they will not be followed for outcomes or toxicities.

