### 12.2 Method and Timing

All patients will be screened for eligibility following consent. Screening must be completed within 30 days of start of therapy. If the time period between screening assessments and start of therapy is greater than 30 days then screening tests must be repeated. The most recent screening labs prior to start of therapy will be considered the

baseline assessment upon which response by the modified IWG criteria will be based. Screening assessments will consist of CBC with differential, ferritin, hepatic and renal function tests and a bone marrow aspirate or biopsy. Women of child bearing potential must have a urine or serum pregnancy test performed within 7 days of start of deferasirox.

Follow up tests will consist of monthly CBC with differential, monthly ferritin levels, and monthly renal and hepatic function tests while the patient remains enrolled in the trial. Bone marrow aspiration or biopsy will be repeated at 3 months and 6 months following the start of deferasirox, and as clinically indicated. If at any point a patient is suspected to have disease progression, a bone marrow biopsy or aspirate may be obtained to document this progression. Physical exams and detailed history will be obtained on a monthly basis to screen for potential toxicities. The primary endpoint of hematologic improvement in the erythroid lineage will be assessed at 6 months following start of deferasirox. The secondary endpoints of hematologic improvement in granulocytes and platelets will also be assessed at 6 months. At the end of 6 months patients who do not respond will be offered the option of alternative treatment options including enrollment into clinical trials if possible.

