## APPENDIX F

## 9422 Study Calendar

Procedure	Screening Phase	Treatment Phase			Follow-up phase		
	Screening within 30 days	Cycle 1 Day 1	Cycle 2-6 Day 1	Cycle 7-12 Day 1	At End of 6 cycles Primary Endpoint	At End of 1 year	30 days after last dose
Medical History	X						
Physical Exam	X	X	X	X	X	X	X
Transfusion History	X	X	X	X	X	X	X
Pregnancy Test*	X						
CBC with differential	X	X	X	X	X	X	X
Serum Creatinine, estimated GFR^	X	X (every 2 weeks)	X	X	X	X	X
Urine protein/creatinine ratio (spot-check)	X				X	X	X
Serum Ferritin	X	X	X	X	X	X	X
Bone Marrow Aspiration or Biopsy	X**		X** (at 3 and 6 months)		X		
Hematologic Improvement according to modified IWG criteria	X	X	X	X		X	
Hepatotrophic Virology¶	X						
Serum transaminases, bilirubin, alkaline phosphatase	X	X (every 2 weeks)	X	X	X	X	X
Auditory and Ophthalmic Testing	X					X	

\*Pregnancy test only in women of child bearing potential may consist of urine or serum pregnancy test and must be completed within 7 days of day 1

^Estimated creatinine clearance with the MDRD formula;

¶Hep B Surface antibody, Hep B surface antigen, Hep C antibody, and HCV PCR

\*\* Research samples: use preservative-free heparin in the syringe and place in sterile, preservative-free red-top tube. Send to hematopathology lab at SCCA

9422

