**APPENDIX G**

**Modified IWG Response Criteria**

**Modified IWG Response Criteria for Hematologic Improvement**

Hematologic Improvement*	Response criteria (responses must last at least 8 wk)†
Erythroid response (pretreatment, < 11 g/dL)	Hgb increase by $\geq 1.5$ g/dL Relevant reduction of units of RBC transfusions by an absolute number of at least 4 RBC transfusions/8 wk compared with the pretreatment transfusion number in the previous 8 wk. Only RBC transfusions given for a Hgb of $\leq 9.0$ g/dL pretreatment will count in the RBC transfusion response evaluation
Platelet response (pretreatment, < $100 \times 10^9$ /L)	Absolute increase of $\geq 30 \times 10^9$ /L for patients starting with $> 20 \times 10^9$ /L platelets Increase from $< 20 \times 10^9$ /L to $> 20 \times 10^9$ /L and by at least 100%†
Neutrophil response (pretreatment, < $1.0 \times 10^9$ /L)	At least 100% increase and an absolute increase $> 0.5 \times 10^9$ /L†
Progression or relapse after HI‡	At least 1 of the following: At least 50% decrement from maximum response levels in granulocytes or platelets Reduction in Hgb by $\geq 1.5$ g/dL Transfusion dependence

Deletions to the IWG response criteria are not shown.

To convert hemoglobin levels from grams per deciliter to grams per liter, multiply grams per deciliter by 10.

Hgb indicates hemoglobin; RBC: red blood cell; HI: hematologic improvement.

\*Pretreatment counts averages of at least 2 measurements (not influenced by transfusions)  $\geq 1$  week apart (modification).

†Modification to IWG response criteria.

[figure not shown]
‡In the absence of another explanation, such as acute infection, repeated courses of chemotherapy (modification), gastrointestinal bleeding, hemolysis, and so forth. It is recommended that the 2 kinds of erythroid and platelet responses be reported overall as well as by the individual response pattern.

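### Is the time at which the primary endpoint is read contradictory, so that one patient's classification could decide the trial?

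*Combined protocol and SAP*

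**What the plan says.** Section 4.2.1 defines the endpoint: "The primary endpoint is the proportion of patients that achieve erythroid hematologic improvement as defined by the modified IWG response criteria at 6 months". Section 12.2 repeats the date: "The primary endpoint of hematologic improvement in the erythroid lineage will be assessed at 6 months following start of deferasirox". Sections 7.3, 7.4 and 12.1 give the same time. Section 7.4 adds what happens next: "At the end of 6 months patients who do not respond will be offered the option of alternative treatments".

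Appendix G sets the response rule. An erythroid response is a haemoglobin rise of at least 1.5 g/dL or a fall of at least 4 red-cell units per 8 weeks, and "responses must last at least 8 wk". A separate row defines "Progression or relapse after HI".

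Appendix F has a column headed "At End of 6 cycles Primary Endpoint". The row "Hematologic Improvement according to modified IWG criteria" is marked at screening, at cycles 1, 2-6 and 7-12, and at one year, but shows no mark in that column.

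One heading in Section 7.3 gives two lengths for the same phase: "Treatment phase (up to 52 weeks: Day 1 to Week 26".

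Section 15.0 tests a null response rate of 0.05 against 0.25 and rejects with 4 or more responses in 25 patients.

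**The concern.** Three things appear to leave the read-out open. The calendar seems to omit the rating at the very visit it labels as the primary endpoint. The Section 7.3 heading ends treatment at both week 26 and week 52. No sentence says how the 8-week duration and the relapse rule relate to month 6. Three classifications can then be imagined:

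- **Complete by month 6:** 8 weeks of response finished at any time up to month 6.
- **Present at month 6:** still in response at month 6, with the preceding 8 weeks complete.
- **Confirmed later:** onset by month 6, with the 8 weeks finished afterwards.

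A late onset counts only under the third. A response completed and then lost before month 6 counts under the first and third but not the second. The trial is open-label and single-arm and turns on 4 of 25. If the choice were made after seeing the data, one patient could decide the result.

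**Working it through.** **1. The date.** Sections 4.2.1, 7.3, 7.4, 12.1 and 12.2 all say 6 months. The Appendix F column says end of 6 cycles, which is the same time. The sources agree on when the endpoint is read. The blank cell is a missing tick: physical examination, transfusion history, blood count and marrow are marked in that column, and Section 7.3 has response data collected monthly. Erythroid response is derived from haemoglobin and transfusions, so the data exist. The table was also machine-read, and the cell would need checking in the original before it supported any inference.

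**2. Which classifications are really open.** Six months is taken as 26 × 7 = 182 days. Eight weeks is 56 days, so a response complete by month 6 must begin by day 182 − 56 = 126. Sections 7.4 and 12.2 identify non-responders at the end of 6 months and offer them alternatives. Status is therefore settled then, and later confirmation fits poorly. Under both remaining classifications an onset after about day 126 does not count, so late onset is not ambiguous between them. They differ only for a patient who completes 8 weeks and relapses before month 6. Section 4.2.1 speaks of patients who achieve improvement, and Appendix G treats relapse as an event following an improvement already attained. Both point to complete by month 6.

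**3. The plan's own figures.** Inputs from Section 15.0: n = 25, reject if X ≥ 4, p0 = 0.05, p1 = 0.25. Formula: P(X ≥ 4) = 1 − [P(0) + P(1) + P(2) + P(3)], with X binomial.

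- At 0.05: 1 − (0.2774 + 0.3650 + 0.2305 + 0.0930) = 0.0341.
- At 0.25: 1 − (0.0008 + 0.0063 + 0.0251 + 0.0641) = 0.904 (0.9038 unrounded).

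The plan prints 0.0336 and 0.9008. Those match a rule that also stops at 0 responses in 15, which the plan does not describe; Section 16.0 says no interim analysis is planned. The gap is small, is a separate matter, and does not affect this point.

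**4. A one-patient shift.**

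- One extra responder in every trial: P(X ≥ 3 at 0.05) = 0.0341 + 0.0930 = 0.1271.
- One fewer responder in every trial: P(X ≥ 5 at 0.25) = 0.9038 − 0.1175 = 0.7863.
- The flip changes the decision only on the boundary: P(X = 3) = 0.093 at 0.05, and P(X = 4) = 0.118 at 0.25.
- One pre-set patient always counted in: P(Bin(24, 0.05) ≥ 3) = 0.116. Always counted out: P(Bin(24, 0.25) ≥ 4) = 0.885.

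**5. A share of responses that depends on the classification.** The documents give no such share, so 10%, 20% and 30% are assumptions.

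| Share lost before month 6 | Power if those are dropped (0.25 × (1 − share)) | Type I error if 0.05 was meant for present at month 6 but they are counted (0.05 ÷ (1 − share)) |
|---|---|---|
| 10% | 0.847 (rate 0.225) | 0.047 (rate 0.0556) |
| 20% | 0.766 (rate 0.200) | 0.067 (rate 0.0625) |
| 30% | 0.660 (rate 0.175) | 0.099 (rate 0.0714) |

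Under any single classification to which the 0.05 null rate applies, the type I error remains 0.034.

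**The case for a change.** The best argument for acting is that a responder rule in an open-label single-arm trial should be fixed before anyone sees data, and that a sentence would do it at no cost in patients or time. Section 2.2 reports a median of 109 days to erythroid response in an earlier deferasirox trial, only 126 − 109 = 17 days before the latest usable onset, so late responders are plausible. The chance of finishing on exactly 3 or 4 responders is not trivial either: 0.12 at a true rate of 0.05, 0.28 at 0.215 and 0.18 at 0.25.

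Part of this stands. No sentence covers a response completed and lost before month 6, or says outright that the 8 weeks must be complete by then. It is also fair that the other calendar rows checked (urine ratio, marrow, hearing and eye tests) broadly follow Table 2, which makes a shift of whole columns unlikely. That does not rule out a lost mark in one row, and the urine row itself carries a mark at 30 days after the last dose that Table 2 does not list.

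The rest is weaker. Section 2.2 does not say whether the 109 days runs to onset or to confirmed response, so it gives no count of late responders. Sensitivity to one patient belongs to any rule of 4 in 25 and is not created by this wording. The alternative classifications would each be acceptable if applied uniformly, so the gap is one of detail and not a stated rule that gives a wrong answer.

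**Conclusion.** The concern does not hold as a contradiction, and no change to the plan follows. The read-out is at 6 months throughout; the empty calendar cell is at most a clerical slip, and the measurements needed are scheduled at that visit. The two durations in the Section 7.3 heading do conflict and must be reconciled as an editorial matter. They do not move the endpoint, because the text beneath that heading states the 6-month assessment separately from the one-year maximum on treatment.

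The remaining gap is the patient whose response lasts 8 weeks and is lost before month 6. An analyst following the text would count a response completed by month 6, keep every enrolled patient in the denominator as the intention-to-treat statement in Section 7.7 implies, and report response still present at month 6 alongside. Following the plan in this way gives a type I error of 0.034 and power of 0.90, provided that the 0.05 and 0.25 of Section 15.0 refer to this endpoint. The 0.127 and 0.79 figures are worst-case bounds that require one patient to be flipped in the same direction in every trial. The actual effect cannot be computed from the documents. This conclusion assumes that month 6 is about day 182 and that one classification is applied to all patients.
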